6. INVESTIGATIONAL MEDICINAL PRODUCT (IMP)

6.1 DOSE AND SCHEDULE

Enrolled patients will receive continuous once-daily oral dosing of vismodegib at a dosage of 150 mg per administration. One cycle of therapy is defined as 28 days of treatment. Dose reduction of vismodegib is not permitted, as there is only a 150-mg capsule strength available.

Dosing of vismodegib will continue until one of the following occurs:

- Investigator-assessed disease progression
- Unacceptable toxicities most likely attributable to vismodegib
- Patient consent withdrawal
- Death
- Reasons deemed by the treating physician
- Study termination by the Sponsor

If there is objective evidence of progressive disease, but the Investigator believes the patient is still deriving benefit from treatment, treatment with vismodegib may be continued after consultation with the medical monitor. However, if there is evidence of further disease progression at the next tumor assessment, vismodegib should be discontinued.

At each study visit, patients will be given enough capsules for dosing until the next study visit. The Investigator is required to confirm that any female patient of childbearing potential has a negative pregnancy test, understands the teratogenic potential of vismodegib, and is using an effective method of contraception prior to dispensing vismodegib. Patients will be instructed to take one 150 mg capsule per day.

Vismodegib should be taken at approximately the same time each day, with or without food. Capsules must be swallowed whole and must not be opened under any circumstances. If a patient misses a dose (e.g., due to emesis), he or she should be instructed not to take or make up that dose and to resume dosing with the next

scheduled dose. Missed doses will not be made up. Patients will be instructed to bring all unused capsules to each study visit for assessment of compliance.

If a patient is suspected to be pregnant, vismodegib must be immediately discontinued. If it is subsequently confirmed that the patient is not pregnant, dosing may be resumed.

The terminal half-life of vismodegib has been determined to be 10–14 days in humans, based on preliminary findings in healthy patients. If plasma concentrations of vismodegib need to be lowered emergently, animal studies suggest that oral administration of activated charcoal may lower plasma drug levels more quickly than dose cessation alone.

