6.3 FORMULATION, PACKAGING, AND LABELING

The formulated drug product vismodegib is provided in hard gelatin capsules of 150 mg. The 150-mg capsules are Size 1 with a grey-colored cap and a pink-colored body. Two black stripes may be printed on the capsule shell using a commercial, compendial grade black ink. Excipients included in the capsule formulations are microcrystalline cellulose, United States Pharmacopeia/National Formulary (USP/NF); lactose monohydrate, USP/NF; sodium lauryl sulfate, USP/NF; Povidone, USP/NF; Talc, USP; sodium glycolate, USP/NF; and magnesium stearate, USP/NF. Capsules are packaged in 75-mL round, white, high-density polyethylene (High-density polyethylene [HDPE]) bottles with two-piece HDPE child-resistant caps. The bottles are induction sealed and labeled for clinical trial use only. Each bottle contains 32 capsules. For additional batch specific instructions and information for vismodegib capsules, see the packaging.

For further details, see the Vismodegib Investigator Brochure.

The packaging and labeling of the study medication will be in accordance with Roche standards and local regulations. Vismodegib will be labeled in compliance with Good Manufacturing Practice (GMP).

Study drug packaging will be overseen by the Roche clinical trial supplies department and bear a label with the identification required by local law, the protocol number, batch number, storage conditions, drug identification and dosage, and the statement, "For Clinical Trial Use Only."

The study drug must be stored according to the details on the product label. The drug label indicates the storage temperature.

Local packaging in some countries may be different.

Upon arrival of investigational products at the site, site personnel should check them for damage and verify proper identity, quantity, integrity of seals and temperature conditions, and report any deviations or product complaints to the monitor upon discovery.

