## **Definition of Last Dose**

Latest date of drug returned where amount taken is greater than 0 and the doses are not missed on this date, in case the dose is missed on this date then take the date of the day before the first dose missed amongst the last group of missed doses.

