## Disposition:

Patients will be considered to have completed the study if they have discontinued or completed treatment, and have completed their follow-up period (1 month for subjects who enrolled to protocol version 1 or 2, or 12 months for subjects who were enrolled to protocol 3 or later).

The reason for discontinuation of the study comes from the End of Follow Up CRF Page and should be listed under reasons for Study Discontinuation based on Safety and Non-safety categories.

Patients discontinued from treatment for a variety of reasons (recorded in the End of Study Treatment CRF page), and these should be listed under reasons for treatment discontinuation based on Safety and Non-safety categories.

Note: under the treatment discontinuation category, those who recorded “withdrew from treatment” in the CRF were assumed to have also left the study (as the investigators were additionally asked for study withdrawal information). As a result, patients who discontinued treatment but remained in follow-up were counted in the “Other” category. A footnote to the discontinuation table should be added to explain this idiosyncrasy.

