## Output Specifications: Safety Outputs

### Exposure:

Capsules are dispensed to each subject at the time of each visit and are recorded on the CRF. Subjects take a dose of 150 mg daily and fill in any missed dose dates on the Patient Diary, in case of dose missed for any reason. The investigator completes the number of capsules taken between visits on the basis of number of capsules returned by the subject at the next visit.

It is possible for a subject to have taken all the dispensed capsules between two visits and still have a missed dose if there is a delay in scheduling or attending the next visit. Consider the total number of capsules dispensed, taken, and the missed dosing date for daily dose calculation (ie, consider the sum of all dispensed/taken doses).

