## Adverse Events:

### General AE Reporting

Listings will include all AEs unless otherwise specified. A Treatment Emergent AE (TEAE) is defined as an AE that starts on or after the first day of study treatment and within 30 days of last dose (please see General Considerations for definition). Unless otherwise specified, AE and SAE summary tables will be restricted to TEAEs.

In STEVIE, the data collection guidelines require that the same AE is entered multiple times into the database, with a separate record for each change in toxicity grade or Lower Level Term. AEs can be reported using this or a “collapsed” Adverse Events analysis dataset.

The Collapsed Adverse Events dataset is derived by combining records that can be reasonably considered to be referring to a single AE term but with changes in toxicity grade (or lower level term). Records from the original AE dataset are grouped, and each group is represented in the collapsed dataset by a single record. The groups are built up by “chaining” records from the original dataset as follows:

- if the Subject ID, System Organ Class and Preferred Term are the same, and
- either the periods defined by the two AEs’ start and end dates overlap, or the Start Date of the later AE is  $\leq 2$  days after the End Date of the earlier one.

In the single record representing the “collapsed” AE:

- Subject ID, System Organ Class and Preferred Term are copied across from any of the records in the group (these are identical so it doesn’t matter which record these variables come from)
- Severity (i.e. toxicity grade) is taken as the most severe grade in the group
- Start Date is taken as the earliest start date in the group
- End Date, Lower Level Term and Outcome are taken from the record with the latest end date in the group

Examples are given on the next page.

Example of derivation of “collapsed” AEs:

Example 1:

SUBJID	System Organ Class	Preferred Term	Lower Level Term	Severity	Outcome	Start Date	End Date
	GASTROINTESTINAL DISORDERS	DYSPEPSI	DYSPEPSIA	GRADE 2 / MODERATE	RESOLVED		
	GASTROINTESTINAL DISORDERS	DYSPEPSI A	HEART BURN	GRADE 3 / SEVERE	RESOLVED		

Collapsed to:

	GASTROINTESTINAL DISORDERS	DYSPEPSI A	HEART BURN	GRADE 3 / SEVERE	RESOLVED		
--	----------------------------	------------	------------	------------------	----------	--	--

Example 2:

SUBJID	System Organ Class	Preferred Term	Lower Level Term	Severity	Outcome	Start Date	End Date

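### The last-dose rule has no provision for a final bottle that is not returned, so exposure is cut short and the 30-day treatment-emergent window can close up to a cycle too early

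*SAP*

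**What the plan says.** SAP, General Considerations, Definition of Last Dose: "Latest date of drug returned where amount taken is greater than 0 and the doses are not missed on this date". The only exception covers a dose missed on the return date, which moves last dose earlier still. Nothing is said about a bottle with no return record.

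SAP, Exposure, explains where the count comes from: "The investigator completes the number of capsules taken between visits on the basis of number of capsules returned by the subject at the next visit". The same paragraph says "Capsules are dispensed to each subject at the time of each visit", so the visit that closes one bottle normally opens the next.

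The date is then used in two places:

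- **Exposure.** Duration is last dose minus first dose plus 1, and person-years are built from duration.
- **Adverse events.** General AE Reporting defines a treatment-emergent event as "an AE that starts on or after the first day of study treatment and within 30 days of last dose" and limits the AE and SAE summary tables to such events by default. Protocol 8.2.2 defines treatment emergence with no upper limit, so the 30-day limit, and with it the dependence on last dose, comes from the SAP.

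A second source on stopping exists. SAP, Disposition: "Patients discontinued from treatment for a variety of reasons (recorded in the End of Study Treatment CRF page"). The SAP listing of premature treatment discontinuation prints the day of last administration and the day of discontinuation as separate columns.

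**The concern.** A patient who dies, is lost to follow-up or simply keeps the last bottle leaves no return date for it. The rule then looks back to the previous return and ignores everything taken since. A patient still dosing at the data cut-off is in the same position.

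AEs, SAEs and exposure are primary variables (Protocol 8.1.1). For an affected patient the error runs one way: last dose too early, duration too short, and the post-treatment tail of the treatment-emergent window shortened or closed.

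**Working it through.** **Inputs.** Let s be the days from dispensing of the unreturned bottle to the true last dose, and t the days from the true last dose to AE start. The dispensing interval is 28 days (Protocol 6.1: "One cycle of therapy is defined as 28 days of treatment"). The capsule limit is 32 (Protocol 6.3: "Each bottle contains 32 capsules"), at one capsule a day. The window is 30 days (SAP, General AE Reporting).

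**1. The SAP's own example.** First dose 1 January, last dose 28 February, 55 capsules taken. The inclusive count is 31 + 28 = 59 days, and 59 − 55 = 4 missed doses, as the SAP states. This confirms that duration counts both end days and that the last-dose date feeds directly into missed doses.

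**2. The derived date.** At visit k the old bottle is returned and counted, and a new one is dispensed. If the new bottle never comes back and no count is entered for it, the latest return with a count above 0 is visit k. Derived last dose = dispensing date of the unreturned bottle; true last dose = that date + s.

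**3. Exposure.** The shortfall is s days, or s/365.25 person-years: 14/365.25 = 0.038, 28/365.25 = 0.077, 32/365.25 = 0.088 per affected patient.

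**4. Treatment-emergent window.** The derived window closes 30 days after dispensing; the correct one closes at s + 30. An event that belongs in the window (t ≤ 30) is lost when s + t > 30.

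| s (days) | Derived close (day) | Correct close (day) | Onset lags t lost |
|---|---|---|---|
| 7 | 30 | 37 | 24–30 |
| 14 | 30 | 44 | 17–30 |
| 21 | 30 | 51 | 10–30 |
| 28 | 30 | 58 | 3–30 |
| 32 | 30 | 62 | 0–30 |

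For s ≤ 30 an event starting on treatment (t = 0) is never lost.

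**5. Illustration only.** Take affected patients whose later events are still reported, with s uniform on 1–28 and whole-day lags uniform. The share lost is 15/196 = 7.7% of events within 7 days of stopping, 78/392 = 19.9% within 14 days, and 406/840 = 48.3% within 30 days. With s uniform on 1–32 the last figure is 525/960 = 54.7%. These are shares of post-treatment events in affected patients, not of all events.

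**6. Patients on treatment at the cut-off.** If the last visit was on schedule, the cut-off lies within about a cycle of dispensing. Events up to the cut-off then fall inside the 30 days, and the effect is essentially on exposure alone.

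**7. What a simple date shift would do.** Extend the SAP example by 14 days from an uncounted bottle: 59 + 14 = 73 days, and 73 − 55 = 18 missed doses. Of these, 18 − 4 = 14 are artefacts. Dose intensity has a related problem already: the unreturned bottle's capsules count as dispensed but not as taken.

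**The case against.** The strongest answer is that the patients who come to mind first lose almost nothing. Treatment-emergent status goes by AE start date. The next visit is due at day 28 ± 3, so a patient who dies before it has a fatal event that began by about day 31, and every onset through day 30 still counts. A patient lost before that visit rarely supplies a later event to lose. A reader might infer that serious or fatal events shortly after stopping are systematically dropped. The documents do not support that. Loss needs a bottle still out, an onset more than 30 days after dispensing, and a report of that event.

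Other points also stand:

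- AE listings include all events by default. The deaths table, the cause-of-death listing and the AE listing for patients who stopped because of death state no treatment-emergent limit.
- The CRF and DAP M3 are not available. The protocol provides a missed-dose diary, accountability at the End of Treatment Visit, a request to return all containers, and contact with a relative when a patient is lost. Some counts may therefore be completed without a routine return.
- A return date later than the true stop pushes last dose the other way in other patients. The net direction over the whole trial is not shown.
- Treatment discontinuation and last administration are different dates. Replacing one by the other without a cap could overextend exposure.

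These limit the size of the problem and shape the remedy. They do not supply the missing rule.

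**Conclusion.** The gap is real. As written, a final bottle not returned, or still out at the cut-off, puts last dose at its dispensing visit. That is too early by 0–28 days in a 28-day cycle and by at most 32 on capsule count. Duration and person-years fall short by the same amount. AEs starting more than 30 days after dispensing but within 30 days of the true last dose can leave the AE and SAE summary tables. Those starting within 30 days of dispensing stay, including events that kill the patient before the next visit.

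This rests on two assumptions: no taken count is entered for an unreturned bottle, and the previous bottle was returned at the visit when the last one was dispensed. The number of such patients is not given, so no effect on incidence can be stated. The SAP's deaths table shows 71 deaths with AE as primary reason among 1215 patients. A reader might take that as the scale of the loss, but nothing links those deaths to unreturned bottles.

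**What to change.** Add to the Definition of Last Dose: if the last dispensed bottle has no return record or a blank taken count, last dose is the earliest available of

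- the treatment-discontinuation date (End of Study Treatment page),
- the date of death,
- the dispensing date plus capsules dispensed minus 1 (for a full bottle, 32 − 1 = 31 days after dispensing), and
- the data cut-off date.

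Use this date for the treatment-emergent window, duration and person-years. Leave the uncounted bottle's period out of the missed-dose and dose-intensity calculations, so that the added days do not become false missed doses. Report how many patients needed the fallback.

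The cost is a short SAP addition and a change to one derivation and its dependent exposure measures, using fields already collected. The downside is that last dose is imputed for these patients, and some events and exposure days move into the on-treatment counts. If the reported number is zero, no result changes.

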## **Reference Date (Study Day 1)**

Where derivations refer to reference date please use date of first dose as there is no randomization date available.

## **Baseline**

Baseline is considered as the most recent time prior to treatment. If a record is collected on the day of first dose, then that record is considered as baseline.

## **Age**

Age is collected on the CRF, but the Age used is the calculated Age. This is defined from the patient's birth date and the patient's consent to the study (both captured on the CRF).

## **Visit Windowing**

Visits are windowed in this study, and all outputs should use the analysis windowed visit as

Study MO25616

Page 2 of 104

opposed to the collected visit unless otherwise specified. The definition of windowing is stored in the DAP M3 (Visit Windowing Spec tab).

### ***Unscheduled Visits***

Visits will be windowed, so any unscheduled visits will be assigned to a visit based upon the collection date. The information about visit windowing is discussed in the Visit Windowing section.

### ***Deaths***

Date of Death can be found on the following pages of the eCRF:

- End of study treatment
- Death page
- Adverse event – end date of AE with grade 5 severity or AE outcome is death
- Serious adverse event – SAE outcome end date; date of death
- End of follow-up page
- Survival follow-up page
- ECOG performance status – status is Grade 5: death

Take the date as defined on the Death page if the sources have different dates, as well as the reason defined on the Death page.

### ***Measurable/Non-Measurable Disease***

A patient is considered to have measurable disease if they have a target lesion at baseline according to the tumour CRF page. This is a 'Yes'/'No' box, but it is not a mandatory field, so some subjects can have a 'missing' result, and such subjects are not considered to have either measurable or non-measurable disease. Measurable/non-measurable disease information is also collected on the CRF disease history page as a tick box, but this information will not be used as the target lesion assessment page is felt to be more accurate.

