8.2.1 Types of Analyses

8.2.1.1 Efficacy Analysis

The efficacy summaries will be presented for the ITT population, which will include all patients enrolled in the study.

The efficacy variable of primary interest for this study is the overall response rate (ORR), as assessed by the Investigator according to RECIST, v1.1. The summary will be

performed on patients with measurable disease at baseline. The best overall response rate (BORR) will be reported. BORR is defined as the number of patients whose best objective response is CR or PR divided by the total number of treated patients in the group for which the BORR is estimated.

Duration of response is the key secondary efficacy variable. It is defined only for the patients whose confirmed best response is CR or PR as the time interval between the date of the earliest qualifying response and the date of PD or death for any cause. For patients who are alive without progression following the qualifying response, duration of response will be censored on the date of last evaluable tumor assessment or last follow-up for progression of disease. This will be done based on Investigator's assessments.

Time to response is defined as the interval between the date of first treatment and the date of first documentation of confirmed CR or PR (whichever occur first). This will be done based on Investigator's assessments.

Progression Free Survival (PFS) is defined as the time interval between the date of the first therapy and the date of progression or death for any causes, whichever occurs first. A patient who died without a reported progression will be considered as an event on the date of death. Patients who have neither progressed nor died will be censored on the date of last evaluable tumor assessment. This will be done based on Investigator's assessments. Patients with non-measurable disease will be assessed for disease progression and included in this summary.

Overall survival (OS) is defined as the time from the date of first treatment to the date of death, regardless of the cause of death. For patients who are alive at the time of analysis, OS time will be censored at the last date the patient was known to be alive. Patients with no post baseline information will be censored at the time of first treatment with vismodegib.

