The best ORRs (confirmed complete and confirmed partial responders) together with the corresponding 95% Pearson-Clopper confidence intervals will be presented. A listing of tumor assessments and best overall response will also be presented.

Estimates for the survivor function for the time-to-event endpoints, including PFS, OS, time to response, and duration of response, will be displayed graphically using Kaplan-Meier (KM) curves. Estimates for the median time to event and the corresponding two-sided 95% confidence interval will be presented with the estimates for the other quartiles and the associated ranges (minimum, maximum). The estimates and KM curves will be presented for the ITT population.

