### **Intent-to-Treat Population (IT)**

The "Intent-to-Treat" population is any patient who took at least one dose of study medication according to the dose accountability CRF page. A patient was considered dosed if they had a 'number of capsules taken' record according to the exposure CRF page that wasn't zero or missing.

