## Progression Free Survival:

TTET01	
Output ID: t_tte_PFS_*
 

● Analysis Population: Intent-to-Treat Patients, excluding patients without histologically confirmed BCC. Outputs will be repeated for different population combinations - please see the LoPO for details of these combinations, and the Efficacy Population section for details on populations.

● Column Variables: Disease Status (Locally Advanced, Metastatic)

● Column Totals: Totals of non-missing Disease Status

● Analysis Variables: Progression Free Survival in Months

● Statistics and Calculation Methods: Use proc freq and proc lifetest.

○ <math>\alpha</math> level for CIs is 2-sided 5%.

○ Use proc lifetest to obtain time to event (Median, Percentiles) information. The 95% confidence interval for the median is calculated using the Brookmeyer & Crowley method.

○ Range, 25th and 75th Percentiles are displayed.

● Numeric Precision and Formatting of Statistics: Use standard display in the mockup

--------	--

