### Programming Note:

- Overall Survival is defined as the interval between the date of first treatment and the date of Death (see above for derivation of date of death).
- Patients who remain alive will be censored at the last date known to be alive.
- N would be the number of patients with a measurable or non-measurable disease at baseline and histologically confirmed BCC.
- Percentages are based on N.
- Patients with a measurable or non-measurable disease at baseline and histologically confirmed BCC are included in the analysis.

For deriving the Date Last Known Alive, please use the standard STREAM default derivation, excluding lab dates.

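### As written, the SAP drops dosed patients with a blank, non-mandatory target-lesion box from the PFS and OS outputs, although those outputs are labelled ITT and neither endpoint depends on measurability

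*SAP*

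**What the plan says.** **Measurability.** The SAP's General Considerations (Measurable/Non-Measurable Disease) use the target-lesion box on the tumour CRF page. On completeness they say that "it is not a mandatory field, so some subjects can have a 'missing' result", and that "such subjects are not considered to have either measurable or non-measurable disease". A second source, a tick box on the disease history page, is set aside: "this information will not be used as the target lesion assessment page is felt to be more accurate".

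**PFS and OS outputs.** The population header of the Progression Free Survival table reads "Intent-to-Treat Patients, excluding patients without histologically confirmed BCC". The Overall Survival table and both Kaplan-Meier plots carry the same restriction and no other. The programming notes under all four outputs say: "Patients with a measurable or non-measurable disease at baseline and histologically confirmed BCC are included in the analysis". The N of the two tables, and the legend counts of the two plots, are defined by the same condition.

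**ITT.** The SAP defines this population as "any patient who took at least one dose of study medication according to the dose accountability CRF page", with no mention of measurability. Protocol Section 8.2.1.1 says: "The efficacy summaries will be presented for the ITT population, which will include all patients enrolled in the study". On the time-to-event endpoints it adds: "The estimates and KM curves will be presented for the ITT population".

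**The concern.** The SAP creates three groups at baseline (measurable, non-measurable, unclassified) and then writes the PFS and OS inclusion rule in terms of the first two. An optional form field therefore decides whether a treated patient contributes to survival. Protocol Section 8.2.1.1 defines OS by death from any cause and PFS by investigator-assessed progression or death, and it expressly keeps non-measurable patients in PFS. Neither endpoint needs a target lesion.

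At stake are the composition of two secondary efficacy analyses and the accuracy of their ITT label. A reader of the tables would see a histology exclusion and nothing else. No table specified in the SAP text has a row for a blank target-lesion field. The disease history table shows measurable status only as Yes or No, and it refers to the disease history page, the source set aside for this purpose. The overall lesion listing covers ITT patients less those without histological confirmation, so a patient with a blank box could appear there with a progression date and yet be absent from PFS.

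**Working it through.** The main check is one of logic, because the plan states no figure on this point.

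1. Blank box: the patient is neither measurable nor non-measurable (SAP, Measurable/Non-Measurable Disease).
2. The disease history tick box may not be used to resolve the blank (same section).
3. Inclusion in PFS and OS requires measurable or non-measurable disease, plus histological confirmation (programming notes for t_tte_PFS, t_tte_OS, g_rs_km_PFS, g_rs_km_OS). The patient fails the first part.
4. The same patient, if dosed, is in the SAP's ITT population and, if histologically confirmed, is admitted by all four headers.

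So header and note define different sets. They differ by exactly the dosed, histologically confirmed patients with a blank box.

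**Illustration of size.** Inputs from the SAP's Summary of Deaths (cut-off 16 March 2015):
- Dosed patients: N = 1119 + 96 = 1215.
- Deaths: D = 92 + 18 = 110.
- Crude mortality: 110/1215 = 9.05%, consistent with the 9.1% printed there.

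The number of blanks, m, is not in the documents; the shares below are assumptions. If m patients are dropped, the crude proportion lies between (D − m)/(N − m), when all of them died, and D/(N − m), when none did.

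| Assumed share blank | m | Remaining | All dropped died | None dropped died |
|---|---|---|---|---|
| 1% | 12 | 1203 | 98/1203 = 8.15% | 110/1203 = 9.14% |
| 2% | 24 | 1191 | 86/1191 = 7.22% | 110/1191 = 9.24% |
| 5% | 61 | 1154 | 49/1154 = 4.25% | 110/1154 = 9.53% |

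If the dropped patients die at the overall rate, the proportion stays at 9.05% in every row.

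The metastatic cohort is more sensitive because it is small: 18/96 = 18.75%. With 2 patients dropped (about 2%), the range is 16/94 = 17.02% to 18/94 = 19.15%.

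These are bounds on a crude proportion among all dosed patients, before the histology exclusion. They are not Kaplan-Meier estimates and are not forecasts.

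**The case against.** The best counter-argument is that the phrase in the notes was meant as 'regardless of measurability', echoing the protocol's statement that non-measurable patients count in PFS. Elsewhere the SAP says 'only' when it wants a restriction, as in the non-measurable best-response table and the duration-of-response plot; the PFS and OS notes do not. That may well have been the intention. It does not settle the matter, because the SAP itself says the two categories do not cover everyone, the N and legend lines repeat the condition, and nothing adds the third group back. If everyone was meant, the correction is only a clarification.

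Second, the PFS and OS tables are to be repeated for population combinations listed in the LoPO, which is not among the documents. An unrestricted version may be listed there. That would soften the consequence but would not reconcile header and note in the outputs specified here.

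Third, PFS and OS are secondary and descriptive (Protocol Sections 8.1.2 and 8.2). Safety is primary, and no decision rule depends on these counts. This stands and limits the importance of the point.

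A reader might also infer that blanks cluster in patients who left or died early, so that dropping them flatters survival. The documents do not support that. They do not say whose boxes are blank, and Protocol Section 5 places the baseline tumour assessment before the first dose (within 7 days for physical examination, 28 for imaging). Every SAP-ITT patient has been dosed, so death or drop-out after dosing is not an obvious cause of a blank baseline field.

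**Conclusion.** The point holds as an inconsistency with a definite consequence: followed literally, the SAP leaves dosed, histologically confirmed patients with a blank target-lesion box out of the PFS and OS tables and plots. This contradicts the outputs' own headers and goes beyond any exclusion the protocol describes for these endpoints.

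Its size cannot be established. The count of blanks is not given, and the bounds above show that crude mortality could move down, move up or not move at all. An upward bias in PFS or OS should not be claimed. With 1% blank, the bounds are at most about 0.9 percentage points below the full-set figure (9.05% − 8.15%) and 0.1 above it (9.14% − 9.05%). The larger movements need more blanks or apply to the small metastatic cohort.

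Nor should one infer that removing the condition would restore the protocol's ITT. The protocol counts all enrolled patients, the SAP's ITT counts dosed patients, and the headers disclose a further histology exclusion. What would be restored is the population that the SAP's headers announce.

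**What to change.** In t_tte_PFS, t_tte_OS, g_rs_km_PFS and g_rs_km_OS, delete the measurable/non-measurable condition from the inclusion statement and from the N and legend definitions. State that every ITT patient admitted by the header is included whatever the target-lesion field contains, including missing. Report the number of patients with a missing field by disease status, for example in a footnote.

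Leave the measurability source for the response outputs as the SAP has it. Measurability does matter there, and the SAP gives a reason for preferring the target-lesion page over the disease history tick box.

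The cost is one condition removed from four outputs and one extra count. No new data are needed.
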